## LIST OF ABBREVIATIONS

RCT	Randomised controlled trial
DSME	Diabetes Self-Management Education
BMI	Body Mass Index
MRC	Medical Research Council
LSHTM	London School of Hygiene and Tropical Medicine
CMU	Chiang Mai University
TMG	Trial Management Group
TSC	Trial Steering Committee
CSV	Comma Separated Value
WS	Workstream
HbA1c	Haemoglobin A1c levels
LTFUP	Lost to Follow up
IRB	Institution Review Board

## STATEMENT OF COMPLIANCE

The study will be carried out in accordance with Good Clinical Practice (GCP) as required by the following:

- UK Policy Framework for Health and Social Care Research applicable to clinical trials.
- SI 2004/1031, Schedule 1, Part 2, 8.
- Medicines for Human Use (Clinical Trials) (2004) regulations .

## PROTOCOL SUMMARY

TITLE	A Scalable Solution for Delivery of Diabetes Self-Management Education in Thailand (DSME Thailand)
DESIGN	3 Arm Cluster randomised controlled trial
AIMS	To develop a culturally-tailored DSME program for Thailand and evaluate its clinical and cost-effectiveness under two alternative modes of delivery: nurse-led and peer-led.
OUTCOME MEASURES	
 
1. Biophysical data: HbA1C; blood glucose and lipids; BMI; Waist circumference; blood pressure.
 
2. Psychosocial and lifestyle data: Quality of life (WHOQOLBREF and EQ-5D); depression and stress (Hospital Anxiety and Depression scale and Perceived stress questionnaire); Diabetes knowledge and skills Brief diabetes illness perception questionnaire, Diabetes Self-Management Education and Support (DMSES), Summary of Diabetes self-care activities questionnaire (SDSCA); Diet (24 Hour Food Recall); smoking; physical activity (International Physical Activity Questionnaire).
 
3. Intervention related data: satisfaction with delivery of educational sessions (Modified Medical Interview Satisfaction scale); peer support (Family and Friends subscale of Chronic Illness Resources survey).
 

POPULATION	Patients attending clinics in Chiang Mai and Lampang province in Northern Thailand
ELIGIBILITY	Adults newly diagnosed type 2 diabetes and those with poor controlled type 2 diabetes within three years of diagnosis, across 21 primary care units in the Chiang Mai and Lampang province of Thailand.
INTERVENTION	Educational/behavioural film-based intervention, delivered to health care professionals, health volunteers and newly diagnosed diabetes patients and those with poor control within three years of diagnosis plus family
TRIAL DURATION	36 months

## STUDY SYNOPSIS

Type 2 diabetes is amongst the foremost challenges facing policy makers in Thailand, accounting for considerable death, disability and healthcare expenditure. Under Thailand's strong primary health system, medical management of diabetes is widely available. However, control of blood glucose and other cardiovascular disease risk factors, and regular screening for early detection of complications remain low due to a lack of services for education and counselling to support behavioural changes necessary for good self-management of the condition. A substantial literature documents the effectiveness of Diabetes Self-Management Education (DSME) programs for improving diabetes outcomes, although little high-quality data are available in Thailand, and traditional delivery models (health-professional led one-to-one or small-group sessions) are unlikely to be scalable in Thailand given current human resource and budgetary constraints. Thus, we propose to develop a low-cost DSME program and scalable delivery model for roll-out within the Thai primary care system.

The intervention is based on behaviour-change and social support theories. This will be delivered in monthly group meetings by lay health workers or nurses, and aided by a suite of short films to introduce key topics and stimulate discussion. We will randomise 21 primary care units to offer DSME to adults diagnosed newly diagnosed with type 2 diabetes and those with poor controlled type 2 diabetes diagnosed within the first three years. This will be delivered by lay health workers, nurses (for comparative effectiveness), or usual care. After 12 months, we will compare glycaemic control and cardiovascular risk scores between the three arms. We will conduct cost-effectiveness, process and policy evaluations to produce best-buy recommendations for the Thai Ministry of Public Health.

[figure not shown]
Through our 3-arm trial design, we will be able to compare effectiveness of nurse-, peer-delivered and standard care, and this along with the process evaluation will provide important lessons for the field of peer-delivery of interventions. In particular, questions remain whether peer educators can be easily trained to effectively deliver state-of-the-art behavioural counselling techniques based on a manualised intervention. The potential for peers to offer long-term support, which might better sustain behaviour change, is also untested and will be investigated through our process evaluation.

While there is much interest in theory-based behaviour change, it is relatively unquestioned whether approaches will be applicable in diverse cultural contexts, which may also have different baseline levels of health education, self-efficacy, social support, etc. Ethnographic observations and follow-up interviews with health workers and participants will explore this issue and produce findings relevant to the psychological theory-based behaviour change field. To ensure that our work reaches a range of academic beneficiaries, we plan to publish our findings in high-impact open access medical, psychological and health policy journals. We will share our study data with other researchers, advertising via our publications and web presence. In particular, we are committed to sharing our findings and data with academic audiences in Thailand and other LMICs.

## SCHEMATIC OF STUDY DESIGN

### Methodology and experimental design annex

Figure 1: Trial flow diagram

## 2. INTRODUCTION: BACKGROUND INFORMATION AND SCIENTIFIC RATIONALE

### 2.1 BACKGROUND INFORMATION

Type 2 diabetes mellitus (hereto referred to as diabetes) is amongst the foremost health challenges facing policy makers in Thailand. The prevalence of diabetes has more than tripled over the last two decades with an estimated 4 million adults (age-adjusted prevalence 7.1%) living with diabetes in 2015.

Diabetes is associated with several macro vascular (e.g. ischaemic heart disease) and microvascular complications (e.g. nephropathy, retinopathy, neuropathy, and foot disease). This primarily accounts for the considerable death and disability (of which diabetes is the 5th leading cause in Thailand), two-fold higher healthcare expenditure, and loss of economic productivity (of persons with diabetes and their carers) associated with this condition in Thailand.

The complications of diabetes can be largely prevented or delayed by good control of their risk factors (blood glucose, lipids and blood pressure), through lifestyle change and medication where necessary, and regular screening for early detection and management of complications.

Under Thailand's universal health coverage, nearly everyone diagnosed with diabetes receives timely medical care (>97%) and has access to screening. Yet, surveys suggest that only about half of the people with diabetes achieve optimal control of risk factors (e.g. HbA1C <7% in 33%, LDL cholesterol <100 mmol/L in 44%, BP <130/80 mmHg in 52%). Alternatively, they receive annual screening for microvascular complications (53-60%). Limited data support a lack of engagement and self-management skills among those diagnosed with diabetes as the main underlying reasons for this.

Successful management of diabetes involves a considerable degree of self-management.

People with diabetes need to adhere to multiple behaviours, including healthy lifestyles, regular monitoring and medication, problem solving and healthy coping. In this, they are greatly supported by diabetes self-management education (DSME), defined as 'a collaborative and ongoing process intended to facilitate the development of knowledge, skills, and abilities that are required for successful self-management of diabetes'. Evidence from over 100 studies, including many randomised controlled trials, conducted predominantly in high-income countries, suggests that DSME programs are associated with improvements in a range of behavioural (knowledge, behaviours, self-efficacy, psychosocial) and clinical (physiological risk factors, screening for complications, quality of life) outcomes, and are also cost-effective; therefore, they are recommended by most clinical guidelines.

Despite this, there is considerable heterogeneity in the effectiveness of DSME programs.

Programs that are more effective usually offer more than 10 hours contact, incorporate behavioural approaches, and provide longer-term support mechanisms. Providing intensive and sustained support however has cost implications, resulting in ongoing efforts to identify more cost-efficient ways to deliver DSME, notably through digital technology (with variable effectiveness) and peers. Peers can support sustained changes in complex health behaviours by providing assistance in daily management, social and emotional support, linkage to clinical care, and ongoing availability of support. Unlike the educational/psychological framework of professional support, peer support operates on a social support framework. Although traditionally restricted to those with experience of disease, the definition of peers has been expanded to include other non-professionals with close relations to the community (e.g. community health workers). However, despite widespread interest, empirical data on effectiveness of peers in supporting behaviour change in chronic diseases, including diabetes, is limited and inconsistent. In an earlier review, the World Health Organisation did not find sufficient evidence to recommend peer support programs as a policy option for diabetes management in LMICs. Data on cost-effectiveness, acceptability and potential adverse consequences of peer support programs from diverse settings, as well as optimal strategies for mobilising and integrating peers in diabetes care pathways, are lacking.

Since the 1960s, community health workers (called village health volunteers) have been a regular part of the Thai healthcare system, linking communities with healthcare providers and providing a range of assistance and

outreach services. The presence of a nationwide network of community health workers (1 million) offers a unique opportunity to develop a scalable model of DSME provision, while building local capacity, and generating critical data on role of peer support programs in LMICs. Taking a similar approach, a multi-country demonstration project in 2010, successfully trained village health volunteers in Thailand for DSME delivery. The study authors reported a substantial engagement and acceptance of the program; however, clinical outcomes could not be robustly evaluated due to fieldwork challenges (before-after data were available for 53 participants only).

In Thai healthcare system, structured DSME is not routinely available (other than brief didactic educational sessions in some centres). While several small-scale studies from Thailand have demonstrated, that DSME can strengthen self-management of diabetes, negative perceptions of educational programs (potentially sustained in the absence of high-quality local data on effectiveness). These concerns about the burden on existing staff time and costs, have so far prevented the introduction of DSME. However, recent policy developments in Thailand are supportive of DSME introduction, if a scalable model can be found. The Thailand Healthy Lifestyles Strategic plan (2011-20) lists reduction of diabetes incidence, complications, disability, mortality, and expense as one of its five main development goals. The current primary healthcare reform of 2017 integrates clinicians, public health staff, and community health workers into primary care clusters to provide community-based and multidisciplinary care; a particular focus is on care of non-communicable diseases and people with disability through improvements in health literacy and self-efficacy.

## 2.2 RATIONALE

The health and economic consequences of Type 2 diabetes mellitus are largely attributable to its complications, which may be prevented or delayed through good disease control. This can be achieved through medical care and self-management. Diabetes Self-Management Education (DSME) programs are effective and cost-effective, and part of standard care in high-income countries, but are unavailable in Thai healthcare system, despite universal coverage of medical aspects of diabetes care. Negative perceptions of educational programs, sustained by a lack of high-quality local data, and concerns about burden on existing staff time and costs are thought to be responsible.

Given the focus on community-based education for chronic diseases in recent primary healthcare reforms, it is timely to scale-up DSME in Thailand, if an affordable model of delivery for a locally-tailored intervention can be found. Taking this opportunity, we propose to work in close collaboration with the Thai Ministry of Public Health to develop, pilot and evaluate a peer-based DSME program and delivery model, finally producing a list of policy recommendations for optimal integration into the Thai healthcare system. Participants will be free to drop into any number of meetings (full or partial) and encouraged to contact their nurse or village health volunteer for advice as necessary. While there is a theoretical risk that this could increase the cost of the program, it is anticipated that it will be regulated by the unwillingness of the participants to attend the program beyond its usefulness; identifying this potential unintended consequence will form part of our process evaluation.

The proposal is to develop a culturally tailored DSME program for Thailand and evaluate its clinical and cost-effectiveness under two alternative modes of delivery: nurse-led and peer-led. While the exact structure of the intervention will be determined by the formative research carried out under this proposal, a low-impact and sustained delivery model is most likely to achieve our twin objectives of long-term behaviour change and scalability.

## 3. STUDY OBJECTIVES

The aim is to identify a scalable model for delivery of DSME across Thailand.

### **Specific project objectives:**

1. To design a prototype of the DSME intervention
2. To refine the intervention prototype and trial design
3. To evaluate the effectiveness and cost effectiveness of intervention under two alternative modes of delivery (nurse-led and peer-led)

4. To identify the most scalable model for DSME delivery in the Thai healthcare system

The primary hypothesis is that either model of DSME delivery will be effective and cost-effective; however, the peer-led model will be a more scalable option for the Thai healthcare system.

## 4. STUDY DESIGN

### 4.1 DESCRIPTION OF THE STUDY DESIGN

This is a four Workstream (WS) programme design based in Thailand aimed at improving cardiovascular risk and control of blood glucose among people with diabetes.

**WS1 and WS2:** Intervention development (content and delivery model) for DSME.

**WS3 and WS4:** A 3-arm cluster randomised trial in primary care units with an inbuilt process and economic evaluation. Twenty-one primary care units will be randomized (seven each) to provide nurse-led DSME, peer-led DSME, or standard care. People with diabetes are the units of analysis. The trial will be unblinded.

#### 4.1.1 STUDY OUTCOME MEASURES

The study outcomes are:

- i. A difference in trial arms at one-year follow-up in HbA1c (co-primary outcome 1)
- ii. A difference in trial aims at one-year follow-up in total cardiovascular risk (co-primary outcome 2)

#### 4.1.2 SETTING

Primary care networks in Chiang Mai and Lampang Province in Northern Thailand, which include 21 primary care units.

## 5. RANDOMISATION

Twenty-one primary care units will be randomized (7 each) to provide nurse-led DSME, peer-led DSME, or standard care (1:1:1). Randomisation will be minimised by primary care networks to account for any variation in practice, although this is expected to be small because it is determined by the tertiary care hospital, which is same for both. The nurses and village health volunteers in intervention arms will be trained to deliver the intervention (at the community hospital or neighbourhoods as appropriate) using training films. No changes will be made to standard care, which currently involves a brief didactic educational session at the time of diagnosis of diabetes. While diabetes is diagnosed at tertiary hospitals, it is managed at, which are served by a full-time nurse (doctor visits weekly), and 10-15 village health volunteers linking patients in the community.

## 6. SELECTION AND WITHDRAWAL OF PARTICIPANTS

All new referrals for diabetes management and those having difficulties managing their diabetes the first three years of diagnosis at the 21 primary units over a 6-month period (N=693) will be recruited to the trial, and offered intervention determined by the trial arm. Prospective participants will be made aware of the study through posters and information sheets. All new referrals will be invited to take part. Local fieldworkers will visit the hospitals and obtain informed consent for study participation. Once consent has been provided, participants will be asked to complete a short questionnaire and to give contact details.

### 6.1 INCLUSION CRITERIA

1. People aged over 18 years with a new referral for type 2 diabetes management at the 21 hospitals

2. People aged over 18 years with difficulties managing diabetes within the first three years of diagnosis at the 21 hospitals.
2. Willingness to attend educational group meetings
3. Available for six and 12-month follow-up

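### Section 10.2.1 leaves baseline adjustment optional and tied to observed imbalance; it should be pre-specified for both co-primary outcomes, and the order of recruitment and arm disclosure should be confirmed.

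*Combined protocol and SAP*

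**What the plan says.** **Analysis.** Section 10.2.1 specifies intention-to-treat analysis of available data, with mixed-effects models to handle clustering by community hospital. On baseline values it commits to nothing: adjustment for imbalance in outcomes or covariates is to be weighed up where suitable, and no covariate is named. Section 4.1.1 gives two co-primary outcomes at one year, HbA1c and total cardiovascular risk. Sections 8 and 9.2 provide for questionnaires, body measurements and blood samples, including HbA1c and lipids, at baseline, 6 and 12 months.

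**Entry.** Section 6.1 admits new referrals and also "People aged over 18 years with difficulties managing diabetes within the first three years of diagnosis at the 21 hospitals". The Protocol Summary describes the second group as "those with poor controlled type 2 diabetes within three years of diagnosis". Neither place gives a value or a source record. Section 6.1 also requires "Willingness to attend educational group meetings" of everyone.

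**Allocation.** Section 4.1 states that "The trial will be unblinded". Section 5 says that "The nurses and village health volunteers in intervention arms will be trained to deliver the intervention", and for the comparator that "No changes will be made to standard care". Under section 6, patients reached over a 6-month period "will be recruited to the trial, and offered intervention determined by the trial arm". Section 6.3 puts consent before enrolment interviews and blood draws. No readable section places randomisation, or disclosure of the arm, before or after those steps. Section 7.1 (WP 3) refers to a trial flow diagram, which is not reproduced in the copy available to this review.

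**The concern.** If the choice between an adjusted and an unadjusted primary analysis is made after looking at the baseline table, two analysts could report different primary results from the same data and both be following the plan. Observed imbalance is also a poor guide to when adjustment helps. The gain depends on how strongly the baseline value predicts the 12-month value, and it is there whether or not the arms happen to differ.

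Recruitment gives a second reason to commit. Randomising units does not protect against differences in who is enrolled once a unit's arm is known. If enrolment followed open allocation, an undefined criterion for difficulty could be applied differently in any arm. A question about willingness to attend meetings could mean something different in a control unit, where none are added. The first would show partly as a baseline severity difference, which adjustment reduces. The second would show as a difference in motivation, which adjustment does not address.

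**Working it through.** **Inputs (section 9.1).** Difference 0.6 HbA1c units, SD 1.5, 7 units per arm, 693 participants, ICC 0.02, 20% loss, 80% power, 2.5% level. Sidedness is not stated; a two-sided level reproduces the plan's total.

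**1. The plan's own figure.**
- Individually randomised size per arm: 2 × [1.5 × (2.241 + 0.842)/0.6]² = 118.8, so 119.
- Analysed per unit with 7 units fixed: 119 × 0.98/(7 − 119 × 0.02) = 116.62/4.62 = 25.2, so 26.
- Recruited per unit: 26/0.8 = 32.5, so 33. Total: 33 × 21 = 693, an exact match.

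**2. Precision without adjustment.**
- Analysed: 33 × 0.8 = 26.4 per unit, and 7 × 26.4 = 184.8 per arm.
- Design effect: 1 + 25.4 × 0.02 = 1.508.
- SE = √(2 × 1.5² × 1.508/184.8) = 0.1916.
- Power at 0.6: Φ(0.6/0.1916 − 2.241) = 81.3%.

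The normal approximation is generous with so few units. Taking 12 df (14 units less 2, a two-arm analysis) or 18 df (21 less 3, one three-arm model), the critical values are 2.560 and 2.445. Noncentral-t power is then 71.1% and 74.8%.

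**3. Precision with adjustment.** The documents give no baseline-to-12-month correlation r, so it is assumed over a range. If r is the same within and between units, SE becomes 0.1916 × √(1 − r²).

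| r | SE | Power, normal | Power, t 12 df | Power, t 18 df |
|---|---|---|---|---|
| none | 0.192 | 81.3% | 71.1% | 74.8% |
| 0.3 | 0.183 | 85.1% | 75.5% | 79.0% |
| 0.5 | 0.166 | 91.5% | 83.8% | 86.8% |
| 0.7 | 0.137 | 98.4% | 95.2% | 96.6% |

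**4. A less favourable case.** Suppose r = 0.5 holds within units only. The squared SE splits into a between-unit part, 2 × 1.5² × 0.02/7 = 0.01286, and a within-unit part, 2 × 1.5² × 0.98/184.8 = 0.02386. These sum to 0.03672 = 0.1916². Only the second part shrinks: 0.01286 + 0.75 × 0.02386 = 0.03076, so SE = 0.175. Power is Φ(0.6/0.1754 − 2.241) = 88%.

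**5. The recruitment order.** No arithmetic applies. Sections 4.1, 5 and 6 fit recruitment after open allocation, but they fit the opposite order equally well. Consent before baseline procedures is settled by section 6.3. Only the placing of randomisation and of arm disclosure is open in the readable text. Section 9.2 describes all 693 as newly diagnosed, so the number entering by the difficulty route cannot be worked out.

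**The case against.** **On adjustment.** The sample size reproduces and reaches 80% power on the plan's approximation without any adjustment, so the trial does not need it to meet its stated target. The correlation is assumed, and the gain is smaller if prediction is weak or confined to within units. All of that stands. It limits the size of the benefit, but gives no reason to let the data decide the primary model. With t reference distributions the unadjusted power is below 80%, so the added precision is useful.

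**On recruitment.** A reader might infer that patients are enrolled with the arm known and that the comparisons are therefore biased. The documents do not support this. The flow diagram may show the order, and its absence from the copy read is not a gap in the plan. Several safeguards are on the page. The opening sentence of section 6 covers both entry routes, which suggests that everyone eligible is to be approached. Fieldworkers rather than unit staff take consent. Individual consent under section 11.2 concerns data collection and blood tests common to all arms. Drop-in attendance (section 2.2) makes willingness a light commitment. What remains is that none of these conceals the arm or defines who counts as having difficulties.

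A reader might also infer that baseline adjustment would cure any selection. It would not: one HbA1c reading captures underlying severity imperfectly and motivation not at all.

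**Conclusion.** The firm finding is about the analysis. Section 10.2.1 makes baseline adjustment optional and linked to observed imbalance, although the measurements are taken in everyone. Committing to it fixes the primary model in advance and costs no participants. On the section 9.1 inputs, power goes from 81% to about 85%, 92% or 98% at r = 0.3, 0.5 or 0.7 under the normal approximation, or to 88% if r = 0.5 holds only within units. With 12 to 18 df, it goes from 71–75% to 84–87% at r = 0.5 (same r within and between units). These figures are for HbA1c; the documents give no SD or target for cardiovascular risk, so its gain cannot be computed.

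The recruitment order is a query, and the undefined entry criterion is a missing definition. Neither shows that selection bias will occur, and the documents give nothing from which its size could be estimated. The sample size itself is internally consistent.

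**What to change.** 1. In section 10.2.1, replace the sentence on baseline imbalance with a commitment: the mixed-effects model for each co-primary outcome will include that outcome's baseline value, whatever imbalance is seen. For total cardiovascular risk, compute the baseline score by the same rule as at 12 months; this assumes that its inputs are among the baseline measures.
2. In sections 5 and 6, confirm from the flow diagram whether eligibility, consent and baseline measurement are complete before the participant is told the arm. If so, repeat it in the text. If not, adopt that order where feasible, with one script in all 21 units.
3. In section 6.1, replace the undefined wording on difficulty with one measurable criterion chosen by the investigators and applied identically in every unit. Include a common rule for patients without a recent record, since section 6.4 describes interim HbA1c as outside routine care.

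Item 1 costs only wording. Item 2 needs modest field organisation and must fit the full explanation that section 11.2 requires before consent; concealment may be imperfect for late recruits where sessions have started. Item 3 may meet some patients without a usable record. Items 1 and 3 still help if concealment fails, though neither deals with differences in motivation.
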